### **2.4 Determination of sample size**

A total of 50 evaluable subjects are planned for enrollment for this study across 2 age groups. The first age group will consist of approximately 40 subjects between 4 years and  $< 18$  years of

age. The second age group will consist of at least 10 subjects between 1 month and <4 years of age. Since the primary objective of this open-label exploratory study is to assess the safety and preliminary efficacy of LCM in subjects with generalized seizures and other epilepsy syndromes, a sample size of 50 evaluable subjects is deemed adequate for meeting the objectives of the study. No formal sample size calculations were performed.

### **3 DATA ANALYSIS CONSIDERATIONS**

#### **3.1 General presentation of summaries and analyses**

Statistical analysis and generation of tables, figures, subject data listings, and statistical output will be performed using SAS Version 9.4 or higher. All tables and listings will use Courier New font size 9.

Descriptive statistics will be displayed to provide an overview of the study results. If not stated otherwise, all summaries will be displayed overall and by age group ( $\geq 1$  month to <4 years,  $\geq 4$  to <12 years, and  $\geq 12$  to <18 years). For categorical parameters, the number and percentage of subjects in each category will be presented. If not stated otherwise, the denominator for percentages will be based on the number of subjects in the respective population. Unless otherwise noted, all percentages will be displayed to 1 decimal place. No percentage will be displayed for zero counts, and no decimal will be presented when the percentage is 100%. For continuous parameters, descriptive statistics will include number of subjects (n), mean, standard deviation (SD), median, minimum, and maximum.

Decimal places for descriptive statistics will always apply the following rules:

- “n” will be an integer.
- Mean, SD, and median will use 1 additional decimal place compared to the original data.
- Coefficient of variance (CV[%]) will be presented with 1 decimal place.
- Minimum and maximum will have the same number of decimal places as the original value.

A complete set of data listings containing all documented data and all calculated data (eg, change from Baseline) will be generated, and will be sorted by site, subject number and visit (where applicable).

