13.2 General statistical considerations

In general, descriptive statistics will be used to provide an overview of the primary, secondary, and other variable results. For categorical parameters, the number and percentage of subjects in each category will be presented. The denominator for percentages will be based on the number of subjects appropriate for the purpose of analysis. For continuous parameters, descriptive statistics will include number of subjects, mean, standard deviation, median, minimum, and maximum.

Unless otherwise specified, Baseline will be based on the last nonmissing data collected prior to the first dose of LCM, ie, assessments on Visit 1 or Visit 2. Baseline of seizure data will be defined as the data collected in the seizure diary during the Baseline Period, ie, from Visit 1 up to 1 day prior to Visit 2.

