#### 3.5.1 Safety Set

The primary analysis set will be the SS and will include all enrolled subjects who take at least 1 dose of LCM.

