### **3.9 Changes to protocol-defined analyses**

Not applicable.

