### **5 STUDY POPULATION CHARACTERISTICS**

#### **5.1 Subject disposition**

The number of subjects screened, and the number and percentage of those subjects who were screen failures, broken down by primary reason for screening failure, will be presented for all subjects screened.

An overall summary of disposition for the SS will present the number and percentage of subjects completing the study and subjects discontinuing along with the reason for discontinuation. This summary will be presented overall as well as for the Titration Period and the Maintenance Period. The disposition summary will be repeated by syndrome subgroups (as described in [Section 4.8](#)).

The number and percentage of subjects who discontinued due to AEs broken down by type of AE will be presented overall only (ie, not by age group). The type of AE will be derived by combining outcome (fatal or not) and seriousness (serious or not) of all these AEs (for several AEs, if applicable) as given in the UCB Standard TFL Shells (see Table DS T 04).

The date of first subject in, date of last subject out, number of screened subjects, and the number of subjects in each analysis set (SS, FAS, and PK-PPS) will be summarized overall and by site for all subjects screened. Subjects who transferred sites will be summarized according to their original site. The summary by site will not be presented by age groups.

Additionally, the number and percentage of subjects in the different analysis sets (SS, FAS, and PK-PPS) will be provided.

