## **8 SAFETY ANALYSES**

All safety analyses will be conducted for the SS.

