### 8.2.2 Adverse events

Treatment-emergent AEs (TEAE) are defined as those events which start on or after the date of first LCM administration and within 30 days following the date of last LCM administration, or whose severity worsens within this time frame.

Other significant AEs are defined in Appendix 13.1 (Table 13-1).

An overall summary of AEs will provide the numbers and percentages of subjects with at least 1 TEAE, serious TEAE, other significant TEAE, TEAE that led to discontinuation, drug-related TEAE, drug-related serious TEAE, severe TEAE, AE leading to death, and TEAE leading to death. The AE overall summary will be repeated by syndrome subgroups (as described in Section 4.8).

The following summaries of AEs will be provided by primary SOC and PT:

- TEAEs
- TEAEs during the Titration Period
- TEAEs during the Maintenance Period
- TEAEs by syndrome subgroups (as described in Section 4.8)
- TEAEs including subject numbers

- Serious TEAEs
- Serious TEAEs including subject numbers
- TEAEs leading to discontinuation
- TEAEs leading to discontinuation including subject numbers
- TEAEs by maximum intensity
- Nonserious TEAEs
- Nonserious TEAEs occurring in > 5% of subjects
- Other significant TEAEs

The following summaries by primary SOC and PT will be presented overall only (ie, not by age group).

- TEAEs by relationship to LCM
- Serious TEAEs by relationship to LCM
- Nonserious TEAEs by relationship to LCM
- Fatal TEAEs by relationship to LCM
- Nonserious TEAEs occurring in at least 5% of subjects by relationship

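### Maintenance Period TEAE percentages default to the whole Safety Set, so they understate the proportion among children who entered Maintenance

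*SAP*

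**What the plan says.** The general rule is in SAP 3.1: "If not stated otherwise, the denominator for percentages will be based on the number of subjects in the respective population". SAP 8 fixes the population for safety: "All safety analyses will be conducted for the SS". Under SAP 3.5.1 the Safety Set "will include all enrolled subjects who take at least 1 dose of LCM"; reaching Maintenance is not required.

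The list of AE tables in SAP 8.2.2 includes "TEAEs during the Maintenance Period" and a matching table for Titration. Neither has a denominator of its own. The SAP defines no Maintenance population: its sets are All Subjects Screened, the SS, the FAS and the PK-PPS.

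SAP 3.2.3 starts the Maintenance Period on the day after Visit 6. A child who terminates early before Visit 6 therefore contributes no Maintenance days.

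Disposition is handled in SAP 5.1: "An overall summary of disposition for the SS will present the number and percentage of subjects completing the study and subjects discontinuing", with reasons. It continues: "This summary will be presented overall as well as for the Titration Period and the Maintenance Period".

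The protocol words the denominator rule differently, in section 13.2: "The denominator for percentages will be based on the number of subjects appropriate for the purpose of analysis". SAP 3.9, headed "Changes to protocol-defined analyses", is marked as not applicable.

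**The concern.** A child who leaves during Titration cannot have a TEAE in the Maintenance Period. If that child stays in the denominator of the Maintenance table, the table treats a child who was never observed there as one observed without an event. The printed percentage is then lower than the proportion among children who were on Maintenance treatment.

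The error runs in one direction only, towards better apparent tolerability, and it grows with the number of children lost in Titration. Such losses are foreseen. Protocol 7.2 provides for withdrawal in Titration when the minimum dose cannot be reached, protocol 6.3 requires withdrawal for intolerable AEs, and SAP 4.2.2 has a rule for subjects who discontinue in Titration. Safety and tolerability is the first study objective. The table is also split by age group, and the youngest group may hold only about 10 children, so a few early exits can move its percentages visibly.

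**Working it through.** **No figure to reproduce.** The documents state no period-specific TEAE rate, no Titration withdrawal rate and no formal sample size calculation. The planned N is the sum of the two age groups, 40 + 10 = 50.

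**Which denominator applies.**
1. SAP 3.1: the respective population, unless stated otherwise.
2. SAP 8: for safety, that population is the SS.
3. SAP 8.2.2: nothing different is stated for the period tables.
4. Where the SAP wants another denominator, it says so: laboratory values (8.5), vital signs (8.6.1), ECG (8.6.2), Tanner stage (8.6.4) and both Global Impression scales (9.1.2, 9.1.3).

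The plain reading is that Maintenance TEAE percentages are taken over the whole SS.

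**Size of the dilution.** Let N be the SS, d the share of the SS leaving in Titration, and x the number of children with a Maintenance TEAE.
- Printed percentage = x / N
- At-risk percentage = x / [N(1 - d)]
- Printed = at-risk × (1 - d)

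Assumptions: N = 50, x = 20, and d from 0 to 30%.

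| d | Entered Maintenance | Printed, 20/50 | At risk | Factor |
|---|---|---|---|---|
| 0% | 50 | 40.0% | 20/50 = 40.0% | 1.0 |
| 10% | 45 | 40.0% | 20/45 = 44.4% | 0.9 |
| 20% | 40 | 40.0% | 20/40 = 50.0% | 0.8 |
| 30% | 35 | 40.0% | 20/35 = 57.1% | 0.7 |

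The same factor applies to each preferred term. With 10 cases and d = 20%, the table prints 10/50 = 20.0% against 10/40 = 25.0%. In an assumed youngest group of 10 with 3 exits and 3 cases, it prints 3/10 = 30% against 3/7 = 43%.

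**Does this push Maintenance below Titration?** Protocol 5.1.1 gives 6 weeks of Titration and 12 of Maintenance. Assume the same weekly hazard in both and a Titration risk p over 6 weeks.
- At-risk Maintenance risk over 12 weeks = 1 - (1 - p)²
- Printed Maintenance risk = [1 - (1 - p)²](1 - d)
- This falls below p only if d > 1 - p / [1 - (1 - p)²] = (1 - p) / (2 - p)

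| Titration risk p | At-risk Maintenance risk | d above which printed Maintenance < Titration |
|---|---|---|
| 10% | 19% | 47% |
| 20% | 36% | 44% |
| 40% | 64% | 38% |
| 60% | 84% | 29% |
| 80% | 96% | 17% |

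At p = 20% and d = 20%, printed Maintenance is 36% × 0.8 = 28.8%, still above Titration. The order of the two tables depends on d, on the hazard and on the doubled follow-up. It is not fixed by the denominator.

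**The case against.** **The denominator is inferred.** No sentence says that the Maintenance TEAE table divides by all SS subjects. Protocol 13.2 allows an at-risk N, and SAP 3.9 declares no change from the protocol. This stands as a caution: the programmed tables may turn out correct. It does not remove the problem, because the SAP has an explicit default and an explicit safety population, and it writes out exceptions elsewhere. Someone following it literally would use the SS.

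**Disposition differs.** Children who leave in Titration appear in SAP 5.1 as Titration discontinuations with a reason, so they are not hidden. A common SS denominator is a normal way to show attrition. This stands. What remains there is labelling: the number entering Maintenance should be visible.

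**A reader can recover the figure.** Counts accompany percentages, disposition gives Titration withdrawals, and SAP 8.4 summarises Maintenance exposure. This limits the harm, but a safety table should not need reworking before it can be read.

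**Stronger readings that do not hold.** A reader might infer that Maintenance rates must look lower than Titration rates. They need not, because Maintenance follow-up is twice as long. A reader might also take the Maintenance table as the test of whether events persist at a stable dose. It is not: SAP 8.2.2 defines TEAEs by start or worsening and gives no rule for assigning an event that continues unchanged across Visit 6. Changing the denominator would not make the table a measure of persistence. Finally, nothing in the documents shows which age group loses most children early.

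**Conclusion.** The point holds for the Maintenance Period TEAE table. Under SAP 3.1 with SAP 8, its percentages equal the at-risk proportions multiplied by (1 - d), so they are too low whenever any child leaves in Titration. For d between 10% and 30% the relative understatement is 10% to 30%. In the illustration above that is 4 to 17 percentage points. The withdrawal shares, the 20 cases and the 50 treated are assumptions; the factor itself is exact.

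The SAP default also sits poorly with protocol 13.2, and SAP 3.9 does not acknowledge a difference.

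The reach is limited. Titration tables, overall TEAEs, serious TEAEs, TEAEs leading to discontinuation and the syndrome tables are not diluted in this way. The study is single-arm and descriptive, so no test or decision rule is affected. The correction should be made because it is cheap and concerns the first objective, but it does not call the safety analysis as a whole into question.

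**What to change.** In SAP 8.2.2, state that percentages in the Maintenance Period TEAE table use SS subjects who entered the Maintenance Period. Define entry as at least 1 day after an actual Visit 6. An early termination visit that SAP 4.2.1 maps to Visit 6 should not count. Show that N in each column header, including the age-group columns. Titration tables keep the SS.

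In SAP 5.1, the disposition table may keep the SS as denominator but should show the number entering Maintenance.

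If the two periods are to be compared, add exposure-adjusted rates, since a corrected denominator does not remove the difference between 6 and 12 weeks.

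The cost is a sentence in each of the two sections, a changed denominator in one table and an added count in another. No new data are needed. Maintenance percentages become somewhat less favourable, and they will describe only children who stayed through Titration, which a footnote should say.

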### **8.1 Primary safety variables**

#### **8.1.1 Generalized spike-wave discharges**

The actual values of generalized spike-wave discharges per interpretable hour on 24-hour ambulatory EEG as well as changes from Baseline will be summarized descriptively by visit.

Furthermore, a frequency table will be presented for the number of subjects with an increase of at least 30% and an increase of at least 50% at Visit 6 compared to Baseline.

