### 8.3 Exploratory safety variables

A frequency table will be presented for the number of subjects with a decrease of at least 30% and a decrease of at least 50% in generalized spike-wave discharges on 24-hour EEG at Visit 6 compared to Baseline by syndrome subgroups

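### Percentages in the 30%/50% EEG frequency tables are taken over the whole Safety Set, so they are diluted by the fraction of children without a usable Baseline and Visit 6 EEG pair

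*SAP*

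**What the plan says.** SAP 3.1 sets two rules that meet in these tables. First: "For categorical parameters, the number and percentage of subjects in each category will be presented". Second, unless something else is stated, "the denominator for percentages will be based on the number of subjects in the respective population".

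SAP 8 opens with "All safety analyses will be conducted for the SS", and the Safety Set (SAP 3.5.1) "will include all enrolled subjects who take at least 1 dose of LCM". Membership needs no EEG.

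The three affected tables are:

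- SAP 8.1.1 (generalized spike-wave discharges), where "a frequency table will be presented for the number of subjects with an increase of at least 30" percent or at least 50 percent at Visit 6 against Baseline.
- SAP 8.2.1 (3Hz discharges), with the same layout.
- SAP 8.3, which counts children with a fall of at least 30 percent or "a decrease of at least 50% in generalized spike-wave discharges on 24-hour EEG at Visit 6 compared to Baseline by syndrome subgroups".

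None of the three names a denominator, requires a paired recording or provides a row for missing recordings. SAP 4.2.2 does not impute these values.

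Other sections of the SAP do override the default. Laboratory (8.5), vital signs (8.6.1), ECG abnormalities (8.6.2) and both global impression scales (9.1.2, 9.1.3) use nonmissing values. Protocol 13.2 has a looser rule: "The denominator for percentages will be based on the number of subjects appropriate for the purpose of analysis".

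**The concern.** A percentage of children whose EEG worsened is naturally read as a rate among children whose EEG could be compared. Under the default it is not. A child without a comparable pair adds one to the denominator and can add nothing to the numerator.

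The study is meant in part to identify syndromes that lacosamide may aggravate (Protocol 5.4), and these tables give the threshold view of the EEG data. An increase percentage that falls as more recordings are lost is a poor guide for that purpose. The same holds for the decrease percentages in 8.3, which are shown by syndrome, where a group may have as few as 4 children (SAP 4.8) and one missing pair moves the figure visibly.

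The pattern of overrides elsewhere suggests an omission rather than a choice.

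**Working it through.** The plan gives no figure to reproduce. It contains no expected worsening rate, no drop-out rate and no missing-EEG rate, and SAP 2.4 says that no formal sample size calculation was made.

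**Who is affected.** Protocol 8.3.4 schedules a 24-hour EEG at the Early Termination (ET) visit. SAP 4.2.1 assigns ET assessments to the next visit at which that assessment is scheduled. For a child who stops during Titration, that visit is Visit 6. The affected children are therefore only those with no usable Visit 2 recording, or with no usable recording at Visit 6 or at a mapped ET visit.

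**Formulas.** Let N be the Safety Set size (or the size of the age or syndrome group), m the number without a usable pair, and k the number meeting the threshold.

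- SAP default: k / N
- Paired-EEG rate: k / (N − m)
- Ratio of the two: (N − m) / N, so the relative understatement is m / N

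**Inputs.** N = 50 is the planned number (SAP 2.4), used here as an illustrative Safety Set. The values of m, and a worsening rate of about 25% among measured children, are assumptions.

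| m | k | SAP default k/50 | Paired rate k/(50 − m) | Gap (points) | Relative shortfall m/50 |
|---|---|---|---|---|---|
| 0 | any | k/50 | k/50 | 0 | 0% |
| 5 | 11 | 22.0% | 11/45 = 24.4% | 2.4 | 10% |
| 10 | 10 | 20.0% | 10/40 = 25.0% | 5.0 | 20% |
| 15 | 9 | 18.0% | 9/35 = 25.7% | 7.7 | 30% |

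**Range over the assumed worsening rate, with m = 10.** The default shows 8.0% for a paired rate of 10% (k = 4), 16.0% for 20% (k = 8), 24.0% for 30% (k = 12) and 32.0% for 40% (k = 16). The relative shortfall is 20% throughout.

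**Smaller groups.**

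- Age group of 10 with 2 missing and 2 worsened: 2/10 = 20.0% against 2/8 = 25.0%.
- Syndrome group of 4 with 1 missing (8.3): with 1 responder, 1/4 = 25.0% against 1/3 = 33.3%; with 2 responders, 2/4 = 50.0% against 2/3 = 66.7%.

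**A related gap.** A child whose Baseline count is zero has no defined percent change, and the SAP gives no rule for this. Under the default such a child also stays in the denominator. The figures above do not include this.

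**The case against.** The strongest reply is that little depends on these tables. Protocol 4.1.1 and 13.3.1 define the primary EEG variable as the change in count, summarized descriptively. SAP 8.1.1 presents that summary first, and SAP 3.1 requires n with every continuous summary, so the number of children with a Visit 6 value appears in the companion output. The threshold table is an addition by the SAP, and no test or stopping rule uses it. All of this stands, and it limits the point to the percentages.

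Four stronger readings are tempting, and the documents do not support them.

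- *The plan classifies missing children as not increased.* It has no such category and no such rule. The effect is arithmetic, through the denominator, and the counts are correct.
- *Children who leave in Titration because their seizures worsen are lost from the table.* Many need not be: an EEG at the ET visit is planned and is mapped to Visit 6.
- *The bias is always reassuring.* It lowers the increase percentages in 8.1.1 and 8.2.1, but in 8.3 it lowers the decrease percentages, which are the favourable ones.
- *The true rate could be far higher because every missing child might have worsened.* That would be informative missingness. A paired denominator would not cure it, so it is no measure of the denominator effect.

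It can also be said that Protocol 13.2 is flexible and that Protocol 13.1 names the Safety Set as the primary analysis set. This is fair: the SAP default does not plainly contradict the protocol. It is, however, a less suitable reading of the protocol's rule than the one the SAP itself adopts for laboratory, vital signs, ECG and global impression data.

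**Conclusion.** The point holds for the percentages in SAP 8.1.1, 8.2.1 and 8.3, and only for those. A stated default, not silence, puts children without an evaluable EEG pair into the denominator, and each percentage falls short of the paired-EEG rate by the missing fraction. Under the assumed 5 to 15 missing of 50 and about 25% worsening, the gap is roughly 2 to 8 percentage points. It is zero if every child has a usable pair or if no child meets the threshold. The actual size cannot be derived from the documents, and the ET mapping makes the affected group smaller than the number of early withdrawals would suggest. The protocol-defined primary summary is not affected.

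**What to change.** In SAP 8.1.1, 8.2.1 and 8.3 add: *Percentages are based on subjects with an interpretable Baseline and Visit 6 (or mapped ET) EEG; the number without an evaluable pair is shown as a separate row.* The same place should say how a zero Baseline count is handled.

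A further row counting withdrawals for seizure worsening as EEG increases is not advised. Withdrawal criterion 9 (Protocol 6.3) concerns clinical seizures, not discharge counts, so such a row would mix two outcomes. Seizure data from children who stop in Titration already enter the other primary variable, because SAP 4.2.2 carries them forward.

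The cost is one sentence in each of three sections and one row per table, with no new data. Where pairs are missing, both the increase and the decrease percentages will come out somewhat higher than under the default.

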#### **3.2 General study level definitions**

##### **3.2.1 Last dose of LCM**

Unless otherwise noted, all references to the last dose of LCM in this SAP refer to the last dose of LCM within the study (eg, including the Taper Period). The last dose of LCM during the Treatment Period will be defined as the last dose during the Titration and Maintenance Periods.

